4.8.2 Sample Size

With respect to safety, 600 subjects exposed to MEDI8897 in Season 1 will provide a 95% probability of observing at least one AE if the true event rate is 0.5%; if no AEs are observed, this study provides 95% confidence that the true event rate is $< 0.5\%$. The sample size is for safety consideration.

With respect to efficacy, approximately 600 subjects will be exposed to MEDI8897 and 300 subjects will be exposed to palivizumab in Season 1 to observe numerically similar efficacy for both mAbs. Because of the reduced incidence of RSV disease in this population following the introduction of palivizumab, a superiority or non-inferiority design is not practical. A valid non-inferiority margin cannot be established due to the lack of historical efficacy data for the medically attended RSV LRTI endpoint for palivizumab. Therefore, there is no hypothesis testing for efficacy. Using an assumption of a 6% RSV LRTI rate in palivizumab recipients, approximately 18 events will be observed in that group. The 6% RSV LRTI rate (1.9% RSV hospitalizations and 3.9% outpatient RSV illness) was based on a prior study in preterm infants with and without CLD who received palivizumab (Carbonell-Estrany et al, 2010). Assuming a 6% rate of RSV LRTI in MEDI8897 recipients, 600 MEDI8897 subjects in Season 1 will provide approximately 36 events in that group. However, because of the largely reduced RSV circulation due to COVID-19 pandemic-related measures, the observed event rates could be much lower. Only summaries will be provided for efficacy unless specified otherwise.

4.8.3 Safety

4.8.3.1 Analysis of Adverse Events

AEs will be graded according to the current version of the NCI CTCAE where applicable for pediatric assessments. AEs will be coded by the Medical Dictionary for Regulatory Activities and the type, incidence, severity, and relationship to study drug will be summarized by treatment group. Other safety assessments will include the occurrence of AESIs defined as AEs of hypersensitivity to study drug (including anaphylaxis), thrombocytopenia, and immune complex disease (eg, vasculitis, endocarditis, neuritis, glomerulonephritis) following study drug administration, and the occurrence of NOCDs following study drug administration.

Safety of MEDI8897 will be summarized by treatment group based on the ATP. The safety summary will be provided for each season, as well as for the 2 consecutive RSV seasons (ie, Season 1 and Season 2). For the Season 1 summary, the analysis dataset will include subjects from the preterm cohort and CLD/CHD cohort, presented by the treatment received in Season 1; for the Season 2 summary and the 2 consecutive-season summary, the analysis dataset will include subjects from the CLD/CHD cohort, presented by the treatment received through the 2 seasons.

4.8.4 Efficacy

The primary efficacy endpoint is the incidence of medically attended RSV LRTI (inpatient and outpatient) through 150 days post Dose 1 (ie, during a typical 5-month RSV season) in Season 1. The determination of the primary efficacy endpoint will be based on RSV test results (performed centrally using real-time RT-PCR; see Section 4.3.1.2) and objective protocol-defined LRTI criteria (see Table 7 and Table 8), and will be summarized by Season 1

treatment group for all 900 subjects. The 95% CI of the percentage of subjects meeting the primary efficacy endpoint will be presented by treatment group. For subjects with multiple medically attended RSV LRTI events, only the first occurrence will be used in the primary efficacy summary.

In addition, the summary of incidence of RSV LRTI through 150 days post Dose 1 in Season 2 will be provided for the 300 subjects in the CLD/CHD cohort based on the treatment assignments through Season 1 and Season 2: ie, (a) 50 mg MEDI8897 for infants with body weight < 5 kg and 100 mg MEDI8897 for infants with body weight \geq 5 kg (Season 1)/200 mg MEDI8897 (Season 2), (b) palivizumab (Season 1)/200 mg MEDI8897 (Season 2), and (c) palivizumab (Season 1)/palivizumab (Season 2).

The incidence of RSV hospitalization through 150 days after dosing (ie, during the 5-month RSV season) will be summarized by treatment group using a similar strategy as described above for RSV LRTI.

Additional analyses will include summarizing RSV-positive LRTI endpoints using results from either the central laboratory or local laboratory.

All efficacy summaries will be based on the ITT Population.

4.8.5 Analysis of Pharmacokinetics and Anti-drug Antibody

4.8.5.1 Pharmacokinetic Analysis

Individual MEDI8897 and palivizumab serum concentration data will be tabulated by treatment group along with descriptive statistics. PK parameters, eg, maximum observed concentration (C_{max}), AUC, apparent clearance, and $t_{1/2}$ will be estimated using non-compartmental analysis, if data permit.

4.8.5.2 Anti-drug Antibody Analysis

The incidence of ADA to MEDI8897 and to palivizumab will be assessed and summarized by number and percentage of subjects who are ADA positive by treatment group. The impact of ADA on PK, and association with TEAEs and TESAEs, will be assessed.

4.8.6 Exploratory Analyses

4.8.6.1 RSV Neutralizing Antibody

Individual MEDI8897 and palivizumab serum anti-RSV neutralizing antibody levels will be tabulated by treatment group along with descriptive statistics. Anti-RSV neutralizing antibody levels in serum will be summarized by geometric mean titer and geometric mean-fold rise and corresponding 95% CI for each treatment group at each visit. Anti-RSV neutralizing antibody level $t_{1/2}$ will be estimated using non-compartmental analysis, if data permit.

4.8.6.2 RSV Serology

Analysis of anti-RSV antigens antibody levels in serum in MEDI8897 and palivizumab recipients will be summarized by geometric mean titer and geometric mean-fold rise and corresponding 95% CI for each treatment group at each visit. Seroresponses in MEDI8897 and palivizumab recipients will be determined by examining the fold-rise in antibodies to Ga, Gb, and N antigens.

4.8.6.3 Healthcare Resource Utilization and Caregiver Burden

The magnitude of HRU (eg, number of admissions to hospitals and ICUs and duration of stay; number of subjects who require respiratory support and supplemental oxygen and the duration of use; number and types of outpatient visits, eg, ER, urgent care, outpatient clinic; and number of prescription and OTC medications and duration of use) will be summarized overall by treatment group and for subjects with at least one medically attended LRTI (protocol defined) caused by RT-PCR-confirmed RSV.

Caregiver burden (eg, caregiver missed work days, subject absence from day care) for subjects with medically attended LRTI (protocol defined) caused by RT-PCR-confirmed RSV will be summarized by treatment group.

The HRU and caregiver burden summaries will be performed on the ITT Population.

4.8.6.4 RSV Resistance Monitoring

RSV genotypic analysis will report the sequence changes in the mature F protein from all RSV positive isolates compared to contemporary RSV A and RSV B reference strains. Susceptibility of novel RSV variants to MEDI8897 and palivizumab will be tested and compared to control viruses.

4.8.6.5 RSV LRTI Occurring From Day 152 to Day 361

The incidence of medically attended RSV LRTI (inpatient and outpatient) from Day 152 to Day 361 for Season 1 and Season 2 will be based on RSV test results (performed centrally via RT-PCR) and objective clinical LRTI criteria and will be summarized by treatment group.

4.8.7 Independent Data Monitoring Committee

An independent data monitoring committee will review safety data regularly and make recommendations regarding further study conduct.

5 ASSESSMENT OF SAFETY

5.1 Definition of Adverse Events

An adverse event is the development of any untoward medical occurrence in a subject or clinical study subject administered a medicinal product and which does not necessarily have a

causal relationship with this treatment. An AE can therefore be any unfavorable and unintended sign (eg, an abnormal laboratory finding), symptom (eg, nausea, chest pain), or disease temporally associated with the use of a medicinal product, whether or not considered related to the medicinal product.

The term AE is used to include both serious and non-serious AEs and can include a deterioration of a pre-existing medical occurrence. An AE may occur at any time even if no study treatment has been administered.

Elective treatment or surgery or preplanned treatment or surgery (that was scheduled prior to the subject being enrolled into the study) for a documented pre-existing condition that did not worsen from baseline is not considered an AE (serious or nonserious). An untoward medical event occurring during the prescheduled elective procedure or routinely scheduled treatment should be recorded as an AE or SAE.

5.2 Definition of Serious Adverse Events

An SAE is any AE that:

- Results in death
- Is immediately life-threatening
- Requires inpatient hospitalization or prolongation of existing hospitalization
- Results in persistent or significant disability/incapacity
- Is a congenital anomaly/birth defect in offspring of the subject
- Is an important medical event that may jeopardize the subject or may require medical intervention to prevent one of the outcomes listed above

Medical or scientific judgment should be exercised in deciding whether expedited reporting is appropriate in this situation. Examples of medically important events are intensive treatment in an ER or at home for allergic bronchospasm, blood dyscrasias, or convulsions that do not result in hospitalizations.

5.3 Definition of Adverse Events of Special Interest

An AESI is one of scientific and medical interest specific to understanding of the investigational product and may require close monitoring and rapid communication by the investigator to MedImmune. An AESI may be serious or nonserious. The rapid reporting of AESIs allows ongoing surveillance of these events in order to characterize and understand them in association with the use of this investigational product.

5.3.1 Hypersensitivity, Including Anaphylaxis

Administration of polyclonal immunoglobulin preparations and mAbs has been associated with immediate (type I) hypersensitivity (including anaphylaxis) that occurs during or after dosing. An immediate hypersensitivity reaction is defined as an acute onset of an illness with involvement of the skin, mucosal tissue, or both during administration of investigational product (but does not meet the definition of anaphylaxis). Anaphylaxis is a rare event, usually occurring after subsequent exposure to antigen, and it is most commonly accompanied by severe systemic skin and or mucosal reactions. It is potentially a fatal, systemic allergic reaction that is distinct from simple allergic reactions (eg, rash, pruritus) because of the simultaneous involvement of several organ systems (Sampson et al, 2006). A full definition of anaphylaxis is provided in [Appendix B](#). See Section 5.5 for recording AEs.

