4.5.1.3 Monitoring of Dose Administration

Subjects will be monitored before and after investigational product administration through assessment of vital signs (temperature, blood pressure, heart rate, and respiratory rate). All vital signs should be obtained within 60 minutes prior to dosing, and at 30 minutes (± 5 minutes) and 60 minutes (± 5 minutes) post dose.

As with any biologic product, allergic reactions to dose administration are possible. Therefore, appropriate drugs and medical equipment to treat acute anaphylactic reactions must be immediately available, and study personnel must be trained to recognize and treat anaphylaxis.

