National Institute of Allergy and Infectious Disease and Food Allergy and Anaphylaxis Network define anaphylaxis as a serious allergic reaction that is rapid in onset and may cause death. They recognize 3 categories of anaphylaxis, with criteria designated to capture from 80% of cases (category 1) to > 95% of all cases of anaphylaxis (for all 3 categories).

- 1 Acute onset of an illness (minutes to several hours) with involvement of the skin, mucosal tissue, or both (eg, generalized hives, pruritus or flushing, swollen lips-tongue-uvula) AND AT LEAST ONE OF THE FOLLOWING
 - (a) Respiratory compromise (eg, dyspnea, wheeze-bronchospasm, stridor, reduced peak expiratory flow [PEF], hypoxemia)
 - (b) Reduced blood pressure (BP) or associated symptoms of end-organ dysfunction (eg, hypotonia [collapse], syncope, incontinence)
- 2 Two or more of the following that occur rapidly after exposure to a likely allergen for that patient (minutes to several hours):
 - (a) Involvement of the skin-mucosal tissue (eg, generalized hives, itch-flush, swollen lips-tongue-uvula)
 - (b) Respiratory compromise (eg, dyspnea, wheeze-bronchospasm, stridor, reduced PEF, hypoxemia)
 - (c) Reduced BP or associated symptoms (eg, hypotonia [collapse], syncope, incontinence)
 - (d) Persistent gastrointestinal symptoms (eg, crampy abdominal pain, vomiting)
- 3 Reduced BP after exposure to known allergen for that patient (minutes to several hours):
 - (a) Infants and children: low systolic BP (age specific) or greater than 30% decrease in systolic BP

SIGNATURE PAGE

This is a representation of an electronic record that was signed electronically and this page is the manifestation of the electronic signature

Document Name: d5290c00005-csp-version-2		
Document Title:	D5290C00005 Clinical Study Protocol Version 2	
Document ID:	Doc ID-003966319	
Version Label:	2.0 CURRENT LATEST APPROVED	
Server Date (dd-MMM-yyyy HH:mm 'UTC'Z)	Signed by	Meaning of Signature
31-Mar-2021 17:16 UTC	██████████	Author Approval
31-Mar-2021 19:25 UTC	██████████████████	Content Approval
31-Mar-2021 18:21 UTC	██████████	Content Approval
31-Mar-2021 19:25 UTC	██████████████	Content Approval
31-Mar-2021 19:49 UTC	██████████	Content Approval

Notes: (1) Document details as stored in ANGEL, an AstraZeneca document management system.

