3.7.2 Adverse Events of Special Interest

Adverse events of special interest (AESI) will include targeted AEs of anaphylaxis and other serious hypersensitivity reactions including immune complex disease and AEs of thrombocytopenia. The number and percentage of subjects with AESIs will be summarized by treatment group and by SOC and PT.

Of note, investigators have been requested to identify the AESI in reporting. The primary interpretation of data will be made upon those events with investigator assessment. In addition, a supplementary analysis is conducted which runs the narrow Standardised MedDRA Query (SMQ) for hypersensitivity, the narrow and broad SMQ for anaphylactic reaction, and a study specific query based on compatible PTs for thrombocytopenia and immune complex disease occurring in the database. These SMQs and PTs will be provided by the medical monitor in a separate document before DBL for Primary Analysis.

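### Protocol 5.3.1 confines non-anaphylactic immediate hypersensitivity to onset during the injection, contrary to its own text elsewhere, so investigator-identified AESIs may be under-flagged or flagged inconsistently

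*Protocol*

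**What the plan says.** Protocol Section 5.3.1 gives two timings in consecutive sentences. The first describes "immediate (type I) hypersensitivity (including anaphylaxis) that occurs during or after dosing". The second, the only sentence there that defines an immediate reaction, sets this condition for a sudden illness to qualify: "involvement of the skin, mucosal tissue, or both during administration of investigational product (but does not meet the definition of anaphylaxis".

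Other places bear on the timing or the use of the category:

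- Protocol 4.8.3.1 has "AESIs defined as AEs of hypersensitivity to study drug (including anaphylaxis), thrombocytopenia, and immune complex disease" and places them "following study drug administration, and the occurrence of NOCDs following study drug administration".
- Protocol 5.5.1 has AESIs recorded from dosing through Day 361.
- Protocol 5.7.3.1 lists urticaria, itching, angioedema, rash and breathing signs as signs of immediate hypersensitivity, sets no time limit, and gives parents a card so that they can report them.
- Protocol 4.5.1.3 requires vital signs "at 30 minutes (± 5 minutes) and 60 minutes (± 5 minutes) post dose".
- Protocol 5.3 allows an AESI to be either serious or nonserious. SAP 3.7.2 describes the hypersensitivity part as anaphylaxis and other reactions that are serious.
- SAP 3.7.2 also states: "The primary interpretation of data will be made upon those events with investigator assessment". A MedDRA query analysis is supplementary.

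**The concern.** Every dose is given intramuscularly, at no more than 1.0 mL per injection, so administration itself is brief. An investigator who looks up what counts as an immediate hypersensitivity reaction reaches the defining sentence in 5.3.1. Under it, a skin reaction that begins after the needle is out, without the further signs needed for anaphylaxis, does not qualify. An investigator who reads the sentence before it, or Section 5.7.3.1, would conclude that it does.

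What is at stake is the investigator-identified AESI table. It reports one component of the primary endpoint and carries the SAP's main reading of these events. If sites resolve the contradiction differently, the table partly reflects how each site read the clause. If most follow the literal text, the AESI incidence is too low.

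**Working it through.** **1. One test case through each rule.** Take widespread urticaria 20 minutes after an injection, with no respiratory, blood-pressure or gastrointestinal signs, not meeting any seriousness criterion.

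- Protocol 5.3.1, defining sentence: not an immediate hypersensitivity reaction, because onset was not during administration.
- Protocol 5.3.1, preceding sentence: within the timing described.
- Protocol Appendix B: not anaphylaxis. Category 1 needs skin involvement plus respiratory or circulatory compromise, category 2 needs two or more features "that occur rapidly after exposure to a likely allergen for that patient (minutes to several hours", and category 3 needs reduced blood pressure.
- Protocol 4.8.3.1 and 5.5.1: an AESI if judged hypersensitivity to study drug, since it follows administration and falls in the recording period.
- Protocol 5.7.3.1: a listed sign, to be reported within 24 hours.
- SAP 3.7.2: outside the stated scope because it is not serious, whatever its timing.
- SAP Table 3: a TEAE. SAP 3.7.5: counted in the within-1-day TEAE summary.
- SAP 3.7.3: in the skin-reaction table only if judged related to investigational product.
- SAP 3.7.2, supplementary query: can be retrieved, because the query does not use the protocol's timing clause.

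The same event is therefore an AESI under some passages and not under others, while its status as a TEAE is never in doubt.

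**2. The plan's own figure.** Protocol 4.8.2 says 600 exposed subjects give a 95% probability of at least one AE at a true rate of 0.5%. Check: 1 − (1 − 0.005)^600 = 0.9506. With no events in 600, the one-sided 95% upper limit is 1 − 0.05^(1/600) = 0.498%, consistent with the stated bound. Both statements reproduce, and the wording defect does not alter them.

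**3. Illustration of under-flagging.** Let f be the fraction of true hypersensitivity events that investigators flag. The documents give no value for f, so it is an assumption shown over a range. With a true rate of 0.5% in 600 subjects, the expected flagged count is 600 × 0.005 × f = 3f, and the chance of at least one flagged event is 1 − (1 − 0.005f)^600:

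- f = 1: 3.0 expected, 95.1%
- f = 0.75: 2.25 expected, 89.5%
- f = 0.5: 1.5 expected, 77.7%
- f = 0.25: 0.75 expected, 52.8%
- f = 0.1: 0.3 expected, 25.9%

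A rate near 0.5% is not remote from this programme: Protocol 1.4.1 reports AESIs in 5 of 966 dosed MEDI8897 subjects (5/966 = 0.5%) and 3 of 481 placebo subjects (3/481 = 0.6%) in Phase 2b.

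**4. Between-arm effect.** If f is equal in both arms, the flagged difference is f·p1 − f·p2 = f(p1 − p2). The absolute difference shrinks by f and the ratio is unchanged. Equal f is itself an assumption.

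**The case against.** The strongest reply is that the protocol, read as a whole, does not exclude these reactions. Sections 4.8.3.1, 5.5.1 and 5.7.3.1 all take in events after the injection, and a site would have to follow one clause against all of them. The reply adds that the infant is well covered anyway. Section 4.3.7 has skin reactions assessed whatever their time of onset and requires sites to notify signs of hypersensitivity or allergic reaction within 24 hours. The discontinuation rule in 4.1.6 turns on a hypersensitivity reaction judged related, not on an AESI flag. In Phase 2b, rashes were flagged as AESIs.

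Much of this stands. The defect is a contradiction that leaves classification open, not a settled exclusion. A reader might infer that expedited reporting or discontinuation would fail for these infants. The documents do not support that, because neither rule uses the clause.

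The reply does not remove the contradiction. The restrictive sentence is the one written as a definition, and the first sentence of 5.7.3.1 uses the same term for the event to be reported. The safeguards do not correct the investigator-identified count: the MedDRA query is supplementary, and the skin table holds only reactions judged related. The Phase 2b rashes settle nothing either way, since neither their onset times nor that study's definition is given. Finally, the SAP amendment history says its AESI definition was aligned with a Safety Strategy and Management Plan that is not among these documents, so what sites were told in practice is unknown.

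**Conclusion.** The definition in 5.3.1 is wrong as written, with minor severity. It contradicts the sentence before it and three other sections. Because the SAP relies on investigator identification, post-injection reactions short of anaphylaxis may be left out of the AESI table or flagged unevenly across sites.

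A reader might infer that such reactions drop out of the primary endpoint. They do not: the endpoint in Protocol 2.1 includes all TEAEs, and these events are TEAEs. The exposure is misclassification within one component.

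The size cannot be derived from the documents. The range above rests on an assumed f and an assumed true rate of 0.5%, and shows only how sensitive a rare-event table is to incomplete flagging. Comparing the brief injection with the observed hour would not measure it either, since a share of clock time is not a share of reactions. The conclusion assumes that at least some sites would apply the defining sentence literally.

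**What to change.** Reconcile the passages as follows:

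- In Protocol 5.3.1, replace the timing in the defining sentence with the section's own wording, *during or after* dosing. Leave any explicit onset window to the sponsor. The interval in Appendix B is written for anaphylaxis, and no passage extends it to other reactions.
- Align the scope in SAP 3.7.2 with Protocol 5.3, so that nonserious hypersensitivity is covered in both. Without this, the urticaria example would still fall outside the SAP's description after the protocol is corrected.
- Send sites a short clarification.
- Before database lock, have sites, still blinded, re-check the skin-reaction eCRF pages already collected against the corrected definition and update the AESI flag where needed.

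The cost is one phrase in each document, a site memo and a modest amount of site review. The AESI rate may come out slightly higher in both arms.

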5.3.2 Immune Complex Disease

Immune complex disease can manifest in the form of a number of conditions such as vasculitis, endocarditis, neuritis, glomerulonephritis, serum sickness, and arthralgias. Drug-induced immune complex (type III) hypersensitivity reactions can occur when host immune system generates antibodies to drug resulting in soluble circulating antigen-antibody complexes formation and their deposition in blood vessels. Subsequently this initiates tissue damaging inflammatory reactions mediated by complement and/or leukocytes and mast cells. The pathology and clinical manifestations are dependent on the tissues/organs involved, with vascular, skin and renal tissues being common sites of injury. Common examples of immune complex hypersensitivity reactions are serum sickness (systemic) and Arthus reactions (local). The clinical manifestations of serum sickness include skin rash, fever, malaise, and polyarthralgias or polyarthritis. Symptoms typically develop 1 to 2 weeks after first exposure to antigen and usually resolve in several weeks after withdrawal of the causative agent. Serum sickness needs to be differentiated from other 'serum-sickness-like' reactions that have a similar clinical presentation (eg, viral infections, anti-seizure drugs), but are believed to have different pathogenic mechanisms. Both serum sickness and serum sickness-like reactions have been reported with mAbs (eg, rituximab, infliximab). Clinical presentation and time to onset should be taken into account for the diagnosis and differentiation of these reactions. Diagnosis of these suspected reactions is best confirmed via biopsy of the affected tissues. See Section 5.5 for recording AEs.

